4. STUDY OBJECTIVES

4.1 Part A

Primary Objective

To evaluate the PK of a single subcutaneous (SC) dose of LY3298176, administered as solution formulation (test) versus lyophilized formulation (reference) in healthy subjects.

Secondary Objective

To investigate the safety and tolerability of LY3298176, administered to healthy subjects.

4.2 Part B

Primary Objective

To evaluate the PK of a single intravenous (IV) dose of LY3298176 in healthy subjects.

Secondary Objective

To investigate the safety and tolerability of LY3298176, administered to healthy subjects via IV formulation

4.3 Part C

Primary Objective

To evaluate the safety and tolerability of LY3298176, following multiple SC weekly doses of a solution formulation administered in healthy subjects.

Secondary Objective

To evaluate the PK of LY3298176, administered as a solution formulation.

5. STUDY DESIGN

Study I8F-MC-GPGE (GPGE) is a single-center, Phase 1 study conducted in healthy subjects in 3 parts: Part A is a 2-period, 2-treatment, crossover design evaluating the relative bioavailability of 2 formulations of LY3298176; Part B, a single-arm design evaluating LY3298176 PK with IV administration; and Part C is a placebo-controlled, single-arm design evaluating the safety, tolerability, and PK of LY3298176 titrated, once-weekly for 4 weeks.

5.1 Part A

Part A is a randomized, 2-period, crossover study in healthy subjects to evaluate the relative bioavailability of 5 mg LY3298176, administered as a solution formulation (test), compared to a 5-mg dose administered as lyophilized formulation (reference).

Each subject will provide informed consent for study participation, and will undergo a screening examination within 28 days prior to enrollment.

In each treatment period, subjects will be admitted to the clinical research unit (CRU) on Day -1. On the morning of Day 1, following an overnight fast of at least 8 hours, subjects will receive a single SC dose of LY3298176, administered according to their assigned treatment sequences. Blood samples will be collected predose and up to 480 hours postdose to measure LY3298176 concentrations. At a minimum, subjects will remain in the CRU for 8 days. The investigator (or qualified designee) will review all available inpatient safety data before discharging subjects from the CRU on the morning of Day 8, provided that the subjects are deemed medically fit.

Subjects may be required to remain in the CRU longer than Day 8, at the investigator's discretion. The subjects will return to the CRU for follow-up visits on Days 21 and 35.

There will be a washout period of at least 35 days between doses in Periods 1 and 2. Based on the PK properties of LY3298176 (terminal half-life: approximately 5 days), a washout period of at least 35 days between doses in Periods 1 and 2 is considered adequate. Period 2 will repeat

the same schedule as Period 1 with the Day 35 visit being the final study visit, which will include an antidrug antibody (ADA) sample at least 10 weeks after the first dose.

5.2 Part B

Part B is a single, 0.5-mg IV dose of LY3298176 solution formulation (or lyophilized formulation in absence of solution formulation) administered to healthy subjects.

Each subject will provide informed consent for study participation, and will undergo a screening examination within 28 days prior to enrollment.

Subjects will be admitted to the CRU on Day -1. On the morning of Day 1, following an overnight fast of at least 8 hours, 2 subjects will receive a single IV dose of 0.5 mg LY3298176, administered over 10 minutes. This dose is expected to be safe while also providing plasma concentrations that can be adequately measured over the course of the sampling time period to enable adequate characterization of the PK profile.

- If the dose of 0.5 mg is found to be safe and well-tolerated, then a PK interim analysis will be performed. Based on the results of the interim analysis, if it is noted that LY3298176 concentrations can be adequately quantified, then 4 more subjects will be dosed.
- If the dose of 0.5 mg is found to be safe and well-tolerated, then a PK interim analysis will be performed. Based on the results of the interim analysis, if it is noted that LY3298176 concentrations cannot be adequately quantified, then a dose adjustment (however less than 1 mg) may be considered for an additional 6 subjects.
- If the dose is not tolerated due to extensive gastrointestinal (GI) events, a lower dose of 0.25 mg (infused over 10 minutes) may be administered to an additional 6 subjects.

Plasma samples will be collected multiple times, including predose and up to 336 hours postdose, to measure LY3298176 concentrations.

At a minimum, subjects will remain in the CRU for 8 days. The investigator (or qualified designee) will review all available inpatient safety data before discharging subjects from the CRU on the morning of Day 8, provided that the subjects are deemed medically fit. Subjects may be required to remain in the CRU longer than Day 8, at the investigator's discretion.

Each subject will be required to return to the CRU for a follow-up visit at least 35 days after the LY3298176 dose. In addition, subjects will need to attend a study visit on Day \geq 70 for an ADA follow-up sample.

5.3 Part C

Part C is a randomized, titration study where healthy subjects will be assigned LY3298176 or placebo at a ratio of 3 LY subjects to 1 placebo subjects. The investigator and subject will be blinded to the treatment.

Subjects will receive a treatment regimen of either LY3298176 or placebo to be given as a SC dose on Days 1, 8, 15, and 22, after an overnight fast (at least 8 hours). Subjects randomized to

LY3298176 will receive a 5 mg dose on Day 1 and Day 8, a 7.5 mg dose on Day 15, and a 10 mg dose on Day 22, administered via solution formulation.

Each subject will be required to return to the CRU for outpatient visits and for a follow-up visit on Day \ge 92.

6. TREATMENTS

The following is a list of the study treatment abbreviations that will be used in the TFLs.

Part	Study Treatment Name	Treatment order in TFL
Α	5 mg LY3298176 SC (lyophilized)	1
	5 mg LY3298176 SC (solution)	2
В	0.5 mg LY3298176 IV	3
С	Placebo SC	4
	5-10 mg LY3298176 SC ¹	5

¹ Subjects receive 5 mg LY3298176 SC on Day 1 and Day 8, 7.5 mg LY3298176 SC on Day 15, and 10 mg LY3298176 SC Day 22

7. SAMPLE SIZE JUSTIFICATION

Approximately 20 healthy subjects may be enrolled in Part A in order that at least 16 subjects complete Part A. Up to 10 subjects will be enrolled in Part B in order that at least 6 subjects complete Part B. Approximately 16 healthy subjects may be enrolled in Part C in order that at least 12 subjects complete Part C (in a 3:1 ratio of LY3298176:placebo).

For each study part, any dropout may be replaced so that the targeted numbers of subjects for safety review and data collection may be achieved. The replacement subject will be assigned to receive the treatment of the dropout.

7.1 Part A

Assuming the intra-subject variability (coefficient of variation [CV]) is 30%. Based on this assumption, 16 subjects will provide a precision of 0.227 on a log-scale for the area under the concentration versus time curve (AUC) or the maximum observed drug concentration (C_{max}) with 90% coverage probability. This would result in a 90% probability that the half-width of the 90% confidence interval (CI) of the ratio of the geometric means for AUC and C_{max} is no larger than 20% in natural scale.

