10.3. Statistical Analyses

Statistical analysis of this study will be the responsibility of Eli Lilly and Company (or its designee).

Pharmacokinetic analyses will be conducted on data from all subjects who receive at least 1 dose of the investigational product and who have evaluable PK.

Safety analyses will be conducted for all enrolled subjects, whether or not they completed all protocol requirements.

Unless, otherwise, noted, all tests of treatment effects will be conducted at a 2-sided alpha level of 0.1, and 90% CIs will be calculated.

Additional exploratory analyses of the data will be conducted, as deemed appropriate. Study results may be pooled with the results of other studies for post-hoc analyses.

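### SAP 7.1 converts a log half-width of 0.227 to 20%, but it is about 25% above the estimated ratio and 20% below it; the stated 90% probability holds only on the lower side

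*SAP*

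**What the plan says.** SAP section 7.1 (Part A) rests on one variability assumption: "Assuming the intra-subject variability (coefficient of variation [CV]) is 30"%. It then makes two linked statements.

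- On the log scale, "16 subjects will provide a precision of 0.227 on a log-scale" for AUC or Cmax, "with 90% coverage probability".
- As the result of this on the ratio scale, it claims with the same probability that the CI half-width for the AUC and Cmax ratios "is no larger than 20% in natural scale".

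The second statement names no side of the interval. SAP section 7 gives the numbers behind the 16: "Approximately 20 healthy subjects may be enrolled in Part A in order that at least 16 subjects complete Part A". The corresponding Part A text in Protocol 10.1 is redacted, so SAP 7.1 is the only statement that can be checked.

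**The concern.** A half-width that is symmetric on the log scale is not symmetric once exponentiated: the upper arm is longer than the lower. A single 20% therefore cannot describe both arms of an interval whose log half-width is 0.227, and only the lower arm comes near it.

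SAP 7.1 is the only visible numerical case for the size of Part A. The sizes of Parts B and C are stated not to rest on a calculation (SAP 7.2), and Part A is the only part with planned inference (SAP 9.3.2 and 9.4.13). The arm that is understated is the upper one, where a higher exposure from the new solution formulation would show. SAP section 3 makes the SAP the template for the study report, so the figure could be carried forward.

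**Working it through.** **Inputs**

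- Intra-subject CV 30% and 16 completers (SAP 7.1).
- 90% probability of meeting the half-width (SAP 7.1).
- Two-sided 90% CI: "all tests of treatment effects will be conducted at a 2-sided alpha level of 0.1, and 90% CIs will be calculated" (Protocol 10.3).
- Design: "Part A is a 2-period, 2-treatment, crossover design evaluating the relative bioavailability of 2 formulations of LY3298176" (SAP 5). Log-transformed parameters are analysed with treatment, period and sequence as fixed effects and subject as random (SAP 9.3.2). With 16 completers this leaves 14 error degrees of freedom; a simple paired analysis would leave 15.

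**Formulas**

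Let s be the within-subject SD on the log scale, n the number of completers and d the error degrees of freedom.

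- Half-width with s known for the variance estimate: h0 = t(0.95, d) × s × √(2/n).
- Half-width met with 90% probability: h90 = h0 × √(χ²(0.90, d)/d).
- Probability that the half-width is at most w: P = Pr[χ²(d) ≤ d × (w/h0)²].

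**Step 1. Reproduce 0.227.** Take the CV directly as the log SD (s = 0.30) and d = 15.

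- h0 = 1.753 × 0.30 × √(2/16) = 0.1859.
- h90 = 0.1859 × √(22.31/15) = 0.1859 × 1.2195 = 0.2267.

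This is the SAP's 0.227.

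**Step 2. The same quantity under the planned model.** Here s = √ln(1 + 0.30²) = √ln 1.09 = 0.2936 and d = 14.

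- h0 = 1.761 × 0.2936 × √(2/16) = 0.1828.
- h90 = 0.1828 × √(21.06/14) = 0.1828 × 1.227 = 0.2242.

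Across the four combinations of s and d, h90 runs from 0.222 to 0.229. The log-scale statement is sound.

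**Step 3. Convert to the ratio scale.**

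| Quantity, relative to the estimated ratio | Formula | h = 0.227 | h = 0.2242 |
|---|---|---|---|
| Upper arm | exp(h) − 1 | +25.5% | +25.1% |
| Lower arm | 1 − exp(−h) | −20.3% | −20.1% |
| Half the full width | [exp(h) − exp(−h)]/2 | 22.9% | 22.6% |

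None of these is 20% or less. The lower arm rounds to 20%.

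**Step 4. Probability of 20% or less with 16 completers.**

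| Reading of 20% | Limit w on the log scale | P, planned model (s = 0.2936, d = 14) | P, inputs that give 0.227 (s = 0.30, d = 15) | Range over the four combinations |
|---|---|---|---|---|
| Upper arm | ln 1.2 = 0.1823 | 54.5% | 50.6% | 50–55% |
| Half the full width | arcsinh 0.2 = 0.1987 | 71.8% | 68.9% | 68–73% |
| Lower arm | −ln 0.8 = 0.2231 | 89.5% | 88.1% | 87–91% |

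For example, the first entry is Pr[χ²(14) ≤ 14 × (0.1823/0.1828)²] = Pr[χ²(14) ≤ 13.93] = 0.545.

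**Step 5. Completers needed for 90% probability of at most 20% above the estimate.** With s = 0.2936 and n = 22 (d = 20), h90 = 0.1820, and exp(0.1820) − 1 = 19.96%. With s = 0.30, 23 are needed. For half the full width, 19 to 20 suffice.

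**The case against.** The strongest reply is that this is a slip in one clause. The log-scale precision and its 90% probability are correct. The 20% is evidently the lower-arm conversion, rounded, and on that side the sentence is true to rounding (87–91%). Read literally, a half-width on the ratio scale is half the full interval, for which the probability is 68–73%; the 54% describes the least favourable of three readings and moves to 51% under the inputs that give exactly 0.227. The calculation is also for the minimum of 16 completers. If all of about 20 enrolled subjects completed, half the full width would be within 20% with 91–94% probability. Finally, neither document sets an equivalence margin or acceptance limit for Part A. The ratio and its interval will be reported as they fall.

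Most of this stands as a limit on the consequence. It does not rescue the sentence. SAP 7.1 is written for 16 subjects and names no side, and on either reading other than the lower arm it falls well short of 90% under every convention for SD and degrees of freedom. Even with 20 completers, the upper arm would be within 20% with only 77–82% probability.

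**Conclusion.** The concern holds. The conversion in SAP 7.1 is wrong as written: a log half-width of 0.227 means about 25% above and 20% below the estimated ratio. With 16 completers and a true intra-subject CV of 30%, the chance that the upper limit is within 20% of the estimate is about 54% under the planned model, against the 90% stated.

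These results assume normal errors on the log scale, the CV that the SAP gives, and complete data from both periods in 16 subjects. The choice of SD and degrees of freedom moves the probabilities by a few points and does not change the conclusion. No estimate, interval or decision rule is affected. The defect is an overstated precision in the only visible size justification for Part A; it should be corrected, but it does not threaten the design.

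**What to change.** Replace the final sentence of SAP 7.1 with wording such as: with 16 completers and an intra-subject CV of 30%, there is a 90% probability that the limits of the 90% CI lie within about 20% below and 25% above the estimated ratio of geometric means. The log half-width can be given as 0.224, which follows from the planned model. Keeping 0.227 is also acceptable, since it is slightly conservative and rounds to nearly the same limits.

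The sponsor should confirm that the lower-side reading was the one intended. If so, the sample size stays as it is, and the only cost is one sentence and a slightly less favourable stated figure. If at most 20% above the estimate was intended, 22 to 23 completers would be needed, which is more than the approximately 20 subjects to be enrolled.

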7.2 Parts B and C

The sample size is customary for Phase 1 studies evaluating safety and PK. The sample sizes are not based on statistical calculations. The sample sizes for each part of the study are considered sufficient to evaluate the primary objectives of this study.

8. DEFINITION OF ANALYSIS POPULATIONS

The "Safety" population will consist of all enrolled subjects, whether or not they completed all protocol requirements.

The "Pharmacokinetic" population will consist of all subjects who received at least one dose of study drug and have evaluable PK data.

All protocol deviations that occur during the study will be considered for their severity/impact and will be taken into consideration when subjects are assigned to analysis populations.

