compliance	Adherence to all the study-related requirements, good clinical practice (GCP) requirements, and the applicable regulatory requirements.
confirmation	A process used to confirm that laboratory test results meet the quality requirements defined by the laboratory generating the data and that Lilly is confident that results are accurate. Confirmation will either occur immediately after initial testing or will require that samples be held to be retested at some defined time point, depending on the steps required to obtain confirmed results.
CPK	creatinine phosphokinase
CRP	clinical research physician: individual responsible for the medical conduct of the study. Responsibilities of the CRP may be performed by a physician, clinical research scientist, global safety physician or other medical officer.
CRU	clinical research unit
CSE	clinically significant effect
CT	computed tomography
CV	coefficient of variation
DBP	diastolic blood pressure
DPP-IV	dipeptidyl peptidase IV
ECG	electrocardiogram
eCRF	electronic case report form
enroll	The act of assigning a patient/subject to a treatment. Patients/Subjects who are enrolled in the study are those who have been assigned to a treatment.
enter	Patients/Subjects entered into a study are those who sign the informed consent form directly or through their legally acceptable representatives.
ERB	ethical review board
FOIA	Freedom of Information Act
FSH	follicle-stimulating hormone
GCP	good clinical practice
GGT	gamma-glutamyltransferase
GI	gastrointestinal
GIP	glucose-dependent insulinotropic polypeptide

Term	Definition
GLP-1	glucagon-like peptide 1
GLP-1 RA	glucagon-like peptide 1 receptor agonist
HIV	human immunodeficiency virus
IB	Investigator's Brochure
ICF	informed consent form
ICH	International Conference on Harmonisation
Ig	immunoglobulin
informed consent	A process by which a patient/subject voluntarily confirms his or her willingness to participate in a particular study, after having been informed of all aspects of the study that are relevant to the patient/subject's decision to participate. Informed consent is documented by means of a written, signed and dated informed consent form.
INR	international normalized ratio
interim analysis	An interim analysis is an analysis of clinical study data, separated into treatment groups, that is conducted before the final reporting database is created/locked.

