9. STATISTICAL METHODOLOGY

9.1 General

Data listings will be provided for all data that is databased. Summary statistics and statistical analysis will only be presented for data where detailed in this SAP. For continuous data, summary statistics will include the arithmetic mean, arithmetic standard deviation (SD), median, min, max and N; for log-normal data (e.g. the PK parameters: AUCs and C_{max}) the geometric mean and geometric CV% will also be presented. For categorical data, frequency count and percentages will be presented. Data listings will be provided for all subjects up to the point of withdrawal, with any subjects excluded from the relevant population highlighted. Summary statistics and statistical analyses will generally only be performed for subjects included in the relevant analysis population. For the calculation of summary statistics and statistical analysis, unrounded data will be used.

Mean change from baseline is the mean of all individual subjects' change from baseline values. Each individual change from baseline will be calculated by subtracting the individual subject's baseline value from the value at the timepoint. The individual subject's change from baseline values will be used to calculate the mean change from baseline using a SAS procedure such as Proc Univariate.

Data analysis will be performed using SAS[®] Version 9.4 or greater.

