9.4 Safety and Tolerability Assessments

9.4.1 Adverse events

Where changes in severity are recorded in the Case Report Form (CRF), each separate severity of the adverse event (AE) will be reported in the listings, only the most severe will be used in the summary tables. A pre-existing condition is defined as an AE that starts before the subject has provided written informed consent and is ongoing at consent. A non-treatment emergent AE is defined as an AE which starts after informed consent but prior to dosing. A treatment-emergent AE is defined as an AE which occurs postdose or which is present prior to dosing and becomes more severe postdose. AEs by day of onset will be presented for Part C.

All AEs will be listed. Treatment-emergent AEs will be summarized by treatment, severity and relationship to the study drug. The frequency (the number AEs, the number of subjects experiencing an AE and the percentage of subjects experiencing an AE) of treatment-emergent AEs will be summarized by treatment, Medical Dictionary for Regulatory Activities (MedDRA) version 20.0 system organ class and preferred term. The summary and frequency AE tables will be presented for all causalities and those considered related to the study drug. Any serious AEs will be tabulated.

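### The Safety population counts subjects from assignment, not from first dose, so any assigned but never-dosed subject would dilute the treatment-emergent AE percentages

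*SAP*

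**What the plan says.** SAP 8 (Definition of Analysis Populations) states that the Safety "population will consist of all enrolled subjects, whether or not they completed all protocol requirements". Protocol 10.3 agrees: "Safety analyses will be conducted for all enrolled subjects, whether or not they completed all protocol requirements". Protocol Appendix 1 fixes the meaning of enrolled: "Patients/Subjects who are enrolled in the study are those who have been assigned to a treatment". None of these texts requires a dose.

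The same section of the SAP does require one for the other analysis set. The Pharmacokinetic "population will consist of all subjects who received at least one dose of study drug and have evaluable PK data".

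Three further texts determine how the Safety population reaches the tables:

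- SAP 9.1: "Summary statistics and statistical analyses will generally only be performed for subjects included in the relevant analysis population".
- SAP 9.4.1, on what counts as an event: "A treatment-emergent AE is defined as an AE which occurs postdose or which is present prior to dosing and becomes more severe postdose".
- SAP 9.4.1, on what is reported by treatment for treatment-emergent AEs: the number of events, and "the number of subjects experiencing an AE and the percentage of subjects experiencing an AE".

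Injection-site reactions are also summarised as incidence or frequency (Protocol 10.3.1.3 for Parts A and C; SAP 9.4.6). SAP 9.4.13 plans no inferential safety analysis.

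**The concern.** The numerator and the denominator of the safety percentages are drawn from different sets. The numerator can contain only dosed subjects, because an event must start or worsen after dosing. The denominator, read from the stated population, contains everyone assigned. An assigned but undosed subject therefore lowers the percentage without having been at risk.

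The documents leave room for such a subject in three ways. A subject may withdraw between assignment and first dose. A dropout may be replaced, and the replacement takes the same treatment (Protocol 10.1, SAP 7), so an undosed dropout and the replacement would both count in one group. Protocol 8.1 and 8.1.1 both provide for an ineligible subject, enrolled by mistake, to stay in the study off study drug; if the mistake is found before dosing, that subject is enrolled and undosed.

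Safety and tolerability is the primary objective of Part C and a secondary objective of Parts A and B. With no safety inference planned, the descriptive summaries are the safety result, and the groups are small enough for one subject to move a percentage visibly.

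**Working it through.** **Group sizes.** The Protocol synopsis gives up to 46 enrolled and 34 completing. The part-level numbers in Protocol 10.1 and SAP 7 reproduce this: 20 + 10 + 16 = 46 and 16 + 6 + 12 = 34. The 3:1 allocation of 16 subjects in Part C gives 12 active and 4 placebo.

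**Formula.** Let a group have N assigned subjects, u of them never dosed, and x dosed subjects with at least one treatment-emergent AE.

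- Percentage with the population as written: x / N.
- Percentage among those at risk: x / (N − u).
- Ratio of the first to the second: (N − u) / N, that is, dosed/enrolled.

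The documents do not say how many subjects, if any, will be assigned and not dosed. The values of u below are assumptions.

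| Group | N assigned | u undosed (assumed) | Factor |
|---|---|---|---|
| Part C placebo | 4 | 1 | 3/4 = 0.75 |
| Part C active | 12 | 1 | 11/12 = 0.917 |
| Part C active | 12 | 2 | 10/12 = 0.833 |
| Part B, minimum completing number | 6 | 1 | 5/6 = 0.833 |
| Part B, maximum enrolled | 10 | 1 | 9/10 = 0.90 |
| Any group | N | 0 | 1 (no effect) |

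**Examples for Part C placebo.**

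- Four assigned, three dosed, one with an event: 1/3 = 33.3% among the dosed becomes 1/4 = 25.0% as written.
- One undosed subject replaced, so five assigned and four dosed, one with an event: 1/4 = 25.0% becomes 1/5 = 20.0%.

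The same factor applies to injection-site reaction percentages in the SC parts, since an undosed subject has no injection site to assess. It does not apply to them in Part B, where dosing is IV.

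**What is not affected.** The counts of events and of subjects with events are unchanged. The Part A comparison of AUC and Cmax uses the PK population, which already requires a dose.

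**Part A by formulation.** A different question is which subjects form the denominator for each formulation when someone is dosed in Period 1 only. SAP 9.4.1 summarises by treatment but states no denominator. Such a subject belongs to an all-enrolled population and equally to an at-least-one-dose population, so changing the population definition does not settle it.

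**The case against.** The strongest reply is that this may never matter. The study is single-center, subjects are admitted the day before dosing, and study drug is given at the site, so an assigned but undosed subject may not arise. SAP 8 adds that protocol deviations are weighed when subjects are placed in populations. SAP 3 refers to a separate document of table shells, not seen here, which may fix the denominators. All AEs are listed, numerators are reported, and disposition is listed, so a reader could recompute any percentage. No planned decision turns on 33% versus 25% in a placebo group of four.

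Much of this stands. It limits the consequence and rules out saying that dilution will occur. It does not remove the defect. The deviation sentence gives discretion but no rule for undosed subjects, and a withdrawal before dosing need not be a deviation. If the shells do use dosed subjects, the SAP should say so. The direction of any effect on the comparison also depends on the arm: an undosed placebo subject widens the apparent active-minus-placebo difference, while an undosed active subject narrows it.

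A reader might go further and infer that missed Part A periods enter the formulation denominators, with the 20 − 16 = 4 allowed non-completers as the measure of dilution. The documents do not support that. They do not place a subject under a formulation never received. Protocol 5.2 defines completion as finishing every scheduled procedure, so someone who received both doses and missed a later visit is a non-completer but dilutes nothing.

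**Conclusion.** The point holds in a limited form and is a minor correction. As written, the Safety population in both documents includes subjects assigned but never dosed, who cannot have a treatment-emergent AE. If one occurs, the affected percentage falls to 0.75 of its value among the dosed in a placebo group of 4, to 0.83 in a Part B group of 6, and to 0.92 in the Part C active group of 12.

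This rests on two assumptions: that at least one assigned subject is never dosed, which the documents allow but do not quantify; and that the AE tables take their denominators from the Safety population, as SAP 9.1 says they generally will. The effect is confined to descriptive safety percentages. For missed Part A periods, only an unstated denominator is shown, not a dilution.

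**What to change.** In SAP 8 and Protocol 10.3, define the Safety population as every subject given one or more doses of study drug, regardless of completion. Report assigned but undosed subjects in disposition only.

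As a separate clarification, add to SAP 9.4.1 and 9.4.6 that in Part A the denominator for each formulation is the number of subjects who received that formulation. The new population definition alone does not supply this.

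If the SAP is changed before the protocol, SAP 11, which now reports no departures from the protocol's analyses, should record the difference. Check the table shells against the new wording.

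The cost is one or two sentences in each document. No new data and no change to the PK analysis are needed.
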